7.1.5.2. Expectedness

A serious adverse event that is not included in the Adverse Reaction section of the relevant reference safety information (RSI) by its specificity, severity, outcome, or frequency is considered an unexpected adverse event. The RSI of the ABS eMDPI in this study is the IB.

A serious adverse event that is not included in the Listing of Adverse Reactions in the IB by its specificity, severity, outcome, or frequency is considered an unexpected adverse event.

The sponsor's Global Patient Safety and Pharmacovigilance (GPSP) will determine the expectedness for all serious adverse events.

For the purpose of suspected unexpected serious adverse reaction (SUSAR) reporting, the version of the IB at the time of occurrence of the SUSAR applies.

7.1.5.3. Reporting a Serious Adverse Event

7.1.5.3.1. Investigator Responsibility

To satisfy regulatory requirements, all serious adverse events that occur during the study, regardless of judged relationship to administration of the test IMP, must be reported to the

sponsor by the investigator. The event must be reported within 24 hours of when the investigator learns about it. Completing the serious adverse event form and reporting the event must not be delayed, even if not all the information is available. The investigator does not need to actively monitor patients for adverse events once this study has ended.

Serious adverse events occurring to a patient after the last administration of IMP of that patient has ended should be reported to the sponsor if the investigator becomes aware of them.

The serious adverse event form should be sent to the local safety officer (LSO) or designee (a contract research organization [CRO] in a country without a sponsor LSO) (contact information is in the Clinical Study Personnel Contact Information section); the LSO will forward the report to the sponsor's GPSP.

The following information should be provided to record the event accurately and completely:

- study number
- investigator and investigational center identification
- patient number
- onset date and detailed description of adverse event
- investigator's assessment of the relationship of the adverse event to the test IMP (no reasonable possibility, reasonable possibility)

Additional information includes:

- age and sex of patient
- date of first dose of IMP
- date and amount of last administered dose of IMP
- action taken
- outcome, if known
- severity
- explanation of assessment of relatedness
- concomitant medication (including doses, routes of administration, and regimens) and treatment of the event
- pertinent laboratory or other diagnostic test data
- medical history
- results of dechallenge/rechallenge, if known
- for an adverse event resulting in death
 - cause of death (whether or not the death was related to IMP)
 - autopsy findings (if available)

Each report of a serious adverse event will be reviewed and evaluated by the investigator and the sponsor to assess the nature of the event and the relationship of the event to the test IMP, study procedures, and to underlying disease.

Additional information (follow-up) about any serious adverse event unavailable at the initial reporting should be forwarded by the investigator within 24 hours of when it becomes known to the same address as the initial report.

For all countries, the sponsor's GPSP will distribute the Council for International Organizations of Medical Sciences form/Extensible Markup Language file to the LSO/CRO for submission to the competent authorities, Independent Ethics Committee/Institutional Review Board (IEC/IRBs), and investigators, according to regulations. The investigator must ensure that the IEC/IRB is also informed of the event in accordance with national and local regulations.

7.1.5.3.2. Sponsor Responsibility

If a serious unexpected adverse event is believed to be related to the test IMP or study procedures, the sponsor will take appropriate steps to notify all investigators participating in sponsored clinical studies of ABS eMDPI and the appropriate competent authorities (and IEC/IRB, as appropriate).

In addition to notifying the investigators and competent authorities (and IEC/IRB, as appropriate), other action may be required, including the following:

- altering existing research by modifying the protocol
- discontinuing or suspending the study
- modifying the existing consent form and informing all study participants of new findings
- modifying listings of expected toxicities to include adverse events newly identified as related to ABS eMDPI

7.1.6. Protocol-Defined Adverse Events not for Expedited Reporting

For purposes of this protocol, there are no anticipated or previously recognized serious adverse events or reactions to be reported to competent authorities in an expedited procedure.

7.1.7. Protocol-Defined Adverse Events of Special Interest

No protocol-defined adverse events of special interest were identified for this study.

7.1.8. Protocol Deviations Because of an Adverse Event

If a patient experiences an adverse event or medical emergency, deviations from the protocol may be allowed on a case-by-case basis. To ensure patient safety, after the event has stabilized or treatment has been administered (or both), the investigator or other physician in attendance must contact the physician identified in the Clinical Study Personnel Contact Information section of this protocol as soon as possible to discuss the situation. The investigator, in consultation with the sponsor, will decide whether the patient should continue to participate in the study.

7.2. Pregnancy

Any female patient becoming pregnant during the study will discontinue the test IMP.

All pregnancies of women participating in the study that occur during the study, within at least 5 half-lives after the end of study are to be reported immediately to the individual identified in the Clinical Study Personnel Contact Information section of this protocol, and the investigator must provide the sponsor (LSO/CRO) with the completed pregnancy form. The process for reporting a pregnancy is the same as that for reporting a serious adverse event but using the pregnancy form (Section 7.1.5.3).

The investigator is not required to report patients who are found to be pregnant between screening and baseline, provided no protocol-related procedures were applied.

All female patients who become pregnant will be monitored for the outcome of the pregnancy (including spontaneous, elective, or voluntary abortion). If the pregnancy continues to term, the outcome (health of the infant up to 8 weeks of age), including details of birth and presence or absence of any birth defect, congenital abnormalities, or maternal and newborn complications, will be reported to the sponsor. Any complication of pregnancy during the study and any complication of pregnancy that the investigator becomes aware of after withdrawal from the study will be reported as an adverse event or serious adverse event, as appropriate.

If the pregnancy in the woman participating in the study does not continue to term, one of the following actions will be taken:

- For a spontaneous abortion, report as a serious adverse event.
- For an elective abortion due to developmental anomalies, report as a serious adverse event.
- For an elective abortion **not** due to developmental anomalies, report on the pregnancy form; do not report as an adverse event.

7.3. Medication Error and Special Situations Related to the Investigational Medicinal Products

Any administration of IMP that is not in accordance with the study protocol should be reported on the CRF either as a violation, if it meets the violation criteria specified in the protocol (Appendix C), or as a deviation, in the patients source documents, regardless of whether or not an adverse event occurs as a result. When meeting protocol violation criteria, all instances of incorrect IMP administration should be categorized on the CRF as "Non-Compliance to investigational medicinal product (IMP)."

The following are types of medication errors and special situations:

- 1. Medication error: Any unintentional error in the prescribing, dispensing, or administration of a medicinal product while in the control of the healthcare professional, patient, or consumer.
- 2. Overdose: Administration of a quantity of a medicinal product given per administration or cumulatively which is above the maximum recommended dose according to the authorized product information. Clinical judgment should always be applied. Any dose of

IMP (whether the test IMP, reference IMP, or placebo IMP), whether taken intentionally or unintentionally, in excess of that prescribed must be immediately reported to the sponsor.

- 3. Misuse: Situations where the IMP is intentionally and inappropriately used not in accordance with the authorized product information.
- 4. Abuse: Persistent or sporadic, intentional excessive use of IMP which is accompanied by harmful physical or psychological effects.
- 5. Off-label use: Situations where an IMP is intentionally used for a medical purpose not in accordance with the authorized product information.
- 6. Occupational exposure: Exposure to an IMP, as a result of one's professional or non-professional occupation.
- 7. Breastfeeding: Suspected adverse reactions which occur in infants following exposure to a medicinal product from breast milk.

7.4. Clinical Laboratory Tests

Any patient who experiences menarche following screening will be required to have a negative urine pregnancy test prior to dosing with IMP. If a patient has a positive urine pregnancy test, then they will be discontinued from the study. Procedures for reporting pregnancy are provided in Section 7.1.5.3.

7.5. Physical Examinations

Physical examinations, including height (to be obtained at the screening visit only) and weight, will be performed at the time points detailed in Table 1.

A physical examination will include, at a minimum, skin, lungs, cardiovascular, respiratory, gastrointestinal, and neurological assessments. Height (to be obtained at the screening visit only) and weight will also be measured and recorded.

Investigators should pay special attention to clinical signs related to previous serious illnesses.

7.6. Vital Signs

Vital signs (blood pressure [systolic/diastolic], respiratory rate, and heart rate) will be measured at the screening visit (Table 1) for inclusion criteria assessment only and will not be used for safety assessment.

7.7. Electrocardiography

Electrocardiogram will not be measured in this study.

8. ASSESSMENT OF PHARMACOKINETICS / PHARMACODYNAMICS / BIOMARKERS / PHARMACOGENOMICS / IMMUNOGENICITY / ANCILLARY STUDIES

Pharmacokinetic, pharmacodynamic, biomarker, pharmacogenomics, immunogenicity, or other ancillary parameters will not be evaluated in this study.

9. STATISTICS

This section describes the statistical analysis as foreseen at the time of planning the study. Changes, additions, and further details about the analyses will be described in the statistical analysis plan. After finalization of the statistical analysis plan, any additional analyses or changes to analyses that may be required will be fully disclosed and justified in the clinical study report (CSR).

9.1. Sample Size and Power Considerations

Assuming an expected dropout rate of 10%, it is recommended that 400 patients be enrolled so that 360 evaluable patients complete the study. The rationale is based on a review of the relevant literature, as follows.

Based on previous studies of a poorly-controlled, exacerbating asthma cohort (Bateman et al 2015, Ko et al 2012, McCarren et al 1998, Quezada et al 2016), it is expected that between 20% and 25% of subjects at risk in this patient population will experience a CAE (event) over 3 months resulting in 72 to 90 expected CAE events in this study. In addition, it is expected that approximately 6.7% and 15% (Bousquet et al 2007, Ko et al 2012, Kuna et al 2007, and Rabe et al 2006) of subjects at risk in this patient population will experience moderate and severe events, respectively, resulting in approximately 78 events (24 moderate events and 54 severe events) in this study.

This sample size (n=400 patients; 72 to 90 CAE events) is considered adequate for fulfillment of the study objectives using univariate and multivariate analyses to evaluate the relationship of the pattern of albuterol use, inspiratory flow, SDI, and TDS data associated with the subsequent development of a moderate CAE or severe CAE. Per the study by Patel (Patel et al 2013b), a statistically significant relationship was established between prior mean daily SABA usage at baseline and subsequent CAE, studying 45 exacerbations (p<0.006).

In the present study, approximately 72 to 90 CAE events are desired for this trial because the model's fitting of the current study involves the analysis of multiple predictors as described in more detail below.

Risk models published in the literature have typically included between 4 and 6 covariates/risk factors (Bateman et al 2015, Greenberg et al 2012, Quezada et al 2016) to examine the relationship between possible risk factors and a disease. When there is more than 1 covariate (risk factor) in the model, multiple logistic regression may be used to estimate the relationship of a specific covariate of interest (ie, albuterol use) to a primary outcome (ie, CAE), adjusting for the other/remaining covariates (risk factors). In this case, the required sample size to estimate such a relationship is greater than that for univariate logistic regression. The number of events per variable has been suggested as a criterion for the size of a data set (Peduzzi et al 1996, Harrell et al 1984, Laupacis et al 1997). The rule of thumb when building logistic regression models is 1 predictor variable for every 10 events (Peduzzi et al 1996, Vittinghoff and McCulloch 2007). Therefore, this sample size would be adequate for predicting the primary outcome (CAE) using multiple logistic regression, including the covariate of primary interest (ie, albuterol use) and the remaining multiple predictors (inspiratory flow values, SDI, and TDS) as potential risk factors for CAE in the model for this patient population.

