Based on previous studies of a poorly-controlled, exacerbating asthma cohort, it is expected that between 20% and 25% of patients at risk in this patient population will experience a CAE (event) over 3 months, resulting in 72 to 90 expected CAE events in this study. In addition, it is expected that approximately 6.7% and 15% of subjects at risk in this patient population will experience moderate and severe events, respectively, resulting in approximately 78 events (24 moderate events and 54 severe events) in the study.

This sample size (n=400 patients; 72 to 90 CAE events) is considered adequate for fulfillment of the study objectives using univariate and multivariate analyses to evaluate the relationship of the pattern of albuterol use, inspiratory flow, SDI, and TDS data associated with the subsequent development of a moderate CAE or severe CAE. Per the study by Patel et al 2013b, a statistically significant relationship was established between prior mean daily SABA usage at baseline and subsequent CAE, studying 45 exacerbations (p<0.006).

In the present study, approximately 72 to 90 CAE events are desired for this trial because the model's fitting of the current study involves the analysis of multiple predictors as described in more detail below.

Risk models published in the literature have typically included between 4 and 6 covariates/risk factors to examine the relationship between possible risk factors and a disease. When there is more than 1 covariate (risk factor) in the model, multiple logistic regression may be used to estimate the relationship of a specific covariate of interest (ie, albuterol use) to a primary outcome (ie, CAE), adjusting for the other/remaining covariates (risk factors). In this case, the required sample size to estimate such a relationship is greater than that for univariate logistic regression. The number of events per variable has been suggested as a criterion for the size of a data set. The rule of thumb when building logistic regression models is 1 predictor variable for every 10 events. Therefore, this sample size would be adequate for predicting the primary outcome (CAE) using multiple logistic regression, including the covariate of primary interest (ie, albuterol use) and the remaining multiple predictors (inspiratory flow values, SDI, and TDS) as potential risk factors for CAE in the model for this patient population.

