Patients will receive initial eMDPI devices at visit 2 and subsequently by courier on Day 21. Patients will be instructed to return all inhalers to the site at the last study visit or early termination. At the last study visit or early termination, patients will be queried for adverse events, concomitant medications, and asthma exacerbations; a physical examination will be completed; and the patient will subsequently be discharged from the trial.

Two subsets of patients who agree to participate at specific sites and wear an accelerometer either on the ankle to measure TDS (n=100) or on the wrist to measure SDI (n=100) will be instructed on the proper use of these devices at the baseline visit (visit 2). The devices will be worn throughout the 12-week intervention period and will be returned to the investigational center at the final visit or upon early termination (visit 5).

The end of study is defined as the last visit of the last patient.

The study duration will be approximately 9 months.

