6.1.3. Inhalational Flow Values Upon Albuterol Dosing

Inhalational flow values will include (1) MIF, (2) inhalational volume, (3) inhalational duration and (4) time to MIF. The inhalational flow data will be downloaded using extraction software directly from eMDPI devices collected from the patients at their final study visit after return of the device to the depot.

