2.3. Sample Size and Power Considerations

Assuming an expected dropout rate of 10%, it is recommended that 400 patients be enrolled so that 360 evaluable patients complete the study. The rationale is based on a review of the relevant literature, as follows.

Based on previous studies of a poorly-controlled exacerbating asthma cohort ([Bateman et al 2015](#), [Ko et al 2012](#), [McCarren et al 1998](#), [Quezada et al 2016](#)), it is expected that between 20% and 25% of subjects at risk in this patient population will experience a CAE (event) over 3 months, resulting in 72 to 90 expected CAE events in this study. In addition, it is expected that approximately 6.7% and 15% ([Bousquet et al 2007](#), [Ko et al 2012](#), [Kuna et al 2007](#), and [Rabe et al 2006](#)) of subjects at risk in this patient population will experience moderate and severe events, respectively, resulting in approximately 78 events (24 moderate events and 54 severe events) in this study.

This sample size (n=400 patients; 72 to 90 CAE events) is considered adequate for fulfillment of the study objectives using univariate and multivariate analyses to evaluate the relationship of the pattern of albuterol use, inspiratory flow, SDI, and TDS data associated with the subsequent development of a moderate CAE or severe CAE. Per the study by Patel ([Patel et al 2013](#)), a statistically significant relationship was established between prior mean daily SABA usage at baseline and subsequent CAE, studying 45 exacerbations ($p < 0.006$).

In the present study, approximately 72 to 90 CAE events are desired for this trial because the model's fitting of the current study involves the analysis of multiple predictors as described in more detail below.

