Risk models published in the literature have typically included between 4 and 6 covariates/risk factors ([Bateman et al 2015](#), [Greenberg et al 2012](#), [Quezada et al 2016](#)) to examine the relationship between possible risk factors and a disease. When there is more than 1 covariate (risk factor) in the model, multiple logistic regression may be used to estimate the relationship of a specific covariate of interest (ie, albuterol use) to a primary outcome (ie, CAE), adjusting for the other/remaining covariates (risk factors). In this case, the required sample size to estimate such a relationship is greater than that for univariate logistic regression. The number of events per variable has been suggested as a criterion for the size of a data set ([Peduzzi et al 1996](#), [Harrell et al 1984](#), [Laupacis et al 1997](#)). The rule of thumb when building logistic regression models is 1 predictor variable for every 10 events ([Peduzzi et al 1996](#), [Vittinghoff and McCulloch 2007](#)). Therefore, this sample size would be adequate for predicting the primary outcome (CAE) using multiple logistic regression, including the covariate of primary interest (ie, albuterol use) and the remaining multiple predictors (inspiratory flow values, SDI, and TDS) as potential risk factors for CAE in the model for this patient population.

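### The adequacy claim rests on 72 to 90 whole-cohort CAEs, but SDI and TDS models draw on about 18 to 25 per subset: models 5 and 6 miss the plan's own rule and models 3 and 4 are marginal

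*Protocol*

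**What the plan says.** Protocol 9.1 plans 400 enrolled patients, 10% dropout and 360 evaluable. It expects 20% to 25% of patients to have a CAE over 3 months, hence 72 to 90 CAEs. Two sentences then claim adequacy. The first is general: "This sample size (n=400 patients; 72 to 90 CAE events) is considered adequate for fulfillment of the study objectives using univariate and multivariate analyses", and it goes on to name albuterol use, inspiratory flow, SDI and TDS. The second follows from a stated criterion, "The rule of thumb when building logistic regression models is 1 predictor variable for every 10 events", and reads: "Therefore, this sample size would be adequate for predicting the primary outcome (CAE) using multiple logistic regression". That sentence then lists all four sets of measures, albuterol use being the one of main interest. The synopsis carries the same text. SAP 2.3 repeats it: "This sample size (n=400 patients; 72 to 90 CAE events) is considered adequate for fulfillment of the study objectives", again with "the remaining multiple predictors (inspiratory flow values, SDI, and TDS) as potential risk factors for CAE in the model".

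The accelerometers do not go to everyone. Under Protocol 3.1, consenting patients at specific sites will "wear an accelerometer either on the ankle to measure TDS (n=100) or on the wrist to measure SDI (n=100"). Protocol 3.2 calls the ankle group a second subset.

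Protocol 9.5.2.1 lists six forward-selection logistic models: (1) albuterol use; (2) albuterol and flow; (3) albuterol and SDI; (4) albuterol and TDS; (5) albuterol, flow and SDI; (6) albuterol, flow and TDS. Demographics, disease state, alternative functional forms and pairwise interactions are further candidates. Flow is not a single variable: "Inhalational flow values will include (1) MIF, (2) inhalational volume, (3) inhalational duration and (4) time to MIF". SAP 7.5.3 and 20.4 pass the predictive modelling to a data analytics group for separate reporting.

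**The concern.** A logistic model can use only patients who have all its predictors. Any model with SDI or TDS is therefore limited to the CAEs in one subset of 100, while the adequacy argument counts the CAEs of the whole cohort. Neither sample-size section gives an expected event count for a subset or applies the 10-event criterion there. Four of the six models are affected.

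The statement is a rationale that later readers will rely on. Someone reading it beside an SDI or TDS result could take that result to have the same support as the albuterol results. The study also has a particular interest in severe CAE, which is rarer, so the subset counts for that outcome are smaller still.

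**Working it through.** **Inputs.** 400 enrolled, 10% dropout, 20% to 25% with a CAE, 6.7% moderate and 15% severe, 10 events per predictor (Protocol 9.1, SAP 2.3). Two separate subsets of 100 (Protocol 3.1, 3.2, 9.5.1). Four flow values (Protocol 6.1.3). SDI is counted as its single composite (Protocol 9.5.1), and TDS and albuterol use as one term each.

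**The plan's own figures.**
- 400 × 0.90 = 360.
- 360 × 0.20 = 72 and 360 × 0.25 = 90.
- 360 × 0.067 = 24.1 moderate and 360 × 0.15 = 54 severe, about 78 in total.

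All reproduce.

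**Whole cohort.** The rule allows 72/10 = 7.2 to 90/10 = 9.0 parameters. Model 2 with albuterol and four flow values has 72/5 = 14.4 to 90/5 = 18.0 events per predictor, which meets the rule.

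**One accelerometer subset.** SAP 4.6 uses data collected before withdrawal, so both ends of 0% to 10% dropout are possible.
- With 10% dropout: 90 × 0.20 = 18 to 90 × 0.25 = 22.5 CAEs.
- Without dropout: 100 × 0.20 = 20 to 100 × 0.25 = 25 CAEs.
- Severe CAE only: 90 × 0.15 = 13.5 to 100 × 0.15 = 15.

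**Events per predictor = subset CAEs / number of terms.**

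| Model | Terms | 10% dropout | No dropout |
|---|---|---|---|
| SDI or TDS alone | 1 | 18 to 22.5 | 20 to 25 |
| 3 or 4 | 2 | 9.0 to 11.25 | 10.0 to 12.5 |
| 3 or 4 plus one candidate | 3 | 6.0 to 7.5 | 6.7 to 8.3 |
| 5 or 6, flow as one term | 3 | 6.0 to 7.5 | 6.7 to 8.3 |
| 5 or 6, four flow values | 6 | 3.0 to 3.75 | 3.3 to 4.2 |

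For severe CAE, two terms give 13.5/2 = 6.75 to 15/2 = 7.5, so a subset supports about one predictor.

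**What would meet the rule.** Two terms need 20 events: 20/0.25 = 80 to 20/0.20 = 100 analysable patients. Three terms need 30 events, or 120 to 150 patients. Six terms need 60 events, or 240 to 300 patients. The plan has 100 per subset.

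**Could recurrent CAEs close the gap?** SAP 7.5.1 allows more than one CAE per patient. Three terms would need an average of 30/25 = 1.2 to 30/18 = 1.7 per exacerbating patient. Six terms would need 60/25 = 2.4 to 60/18 = 3.3. The documents give no recurrence rate.

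**The case against.** **The study is exploratory and the rule is only a rule of thumb.** Both are true, and they limit the seriousness. But the plan itself draws its conclusion from that rule, so the rule can fairly be applied to each model it is said to cover.

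**The SAP removed these models, and the SAP prevails.** The SDI and TDS analyses left in SAP 7.3 and 7.4 are descriptive, so no inference specified in the SAP depends on the claim. This stands as a limit on the consequence. It does not cure the text: SAP 2.3 keeps the statement, and the modelling is still planned elsewhere.

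**The subset size is stated openly.** It is, in several places, and a careful reader could work out the shortfall. The sample-size sections do not do so.

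**The counts depend on choices the plan leaves open.** The number of flow terms is not fixed. Recurrent CAEs would raise the counts. Download failures (SAP 3.4, 3.5) would lower them. Forward selection may retain fewer terms, but it searches all the candidates, and demographic, disease-state and functional-form candidates come on top of those counted here.

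Three stronger readings are tempting and are not supported:
- A reader might infer that the plan still intends one model holding both SDI and TDS. The sentence is loose enough to suggest it, but none of the six models does, and the Amendment 01 rationale in Protocol 16.2 explains that the joint models were deleted because the measures come from subsets.
- A reader might infer that models 3 and 4 fail. With two terms they straddle 10.
- A reader might infer a definite amount of overfitting in the C-statistic. That depends on effect sizes and an entry level that the documents do not give, so no figure is offered.

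**Conclusion.** By the plan's own criterion, the adequacy statement is wrong for models 5 and 6 and not assured for models 3 and 4, where any added candidate takes them below the rule. It holds for models 1 and 2, provided the total number of candidates stays within about 7 to 9, and for univariate use of SDI or TDS against any CAE. The study as a whole is not shown to be too small.

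This rests on four assumptions: the subsets have the cohort's CAE rate, although they consist of volunteers at specific sites; dropout is 0% to 10%; each exacerbating patient contributes one CAE; and SDI is a single term. It should be fixed because the statement is incorrect for planned analyses and cheap to correct. It does not threaten the whole-cohort albuterol analyses.

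**What to change.** Replace both adequacy sentences in SAP 2.3, which has priority because the SAP prevails where the documents differ. The SAP does not list the six models, so describe them in words:

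> With 72 to 90 CAEs expected in the whole cohort, the sample is adequate for univariate analyses of any CAE. At 10 events per predictor it also supports whole-cohort models of albuterol use and inspiratory flow with up to about 7 to 9 candidate parameters in total, counting demographic, disease-state, functional-form and interaction candidates. SDI and TDS are each measured in a separate subset of 100 patients, with about 18 to 25 CAEs (13.5 to 15 severe) expected per subset. Models that add SDI or TDS are hypothesis-generating, and those that also include inspiratory flow values do not meet the rule. SDI and TDS are not entered in one model.

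Align the synopsis and Protocol 9.1 if the protocol is next amended. Protocol 9 already lets the SAP carry changes, so a protocol amendment for this alone is not needed.

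Optional, in the analytics specification: Protocol 9.5.2.1 compares models by C-statistic without naming the sample. Where an SDI or TDS model is compared with model 1 or 2, refit model 1 or 2 in the same subset and report an optimism-corrected C. Whether this is already planned cannot be seen from the documents.

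The cost is a short SAP revision, a less favourable statement about SDI and TDS, and a little extra analysis if the optional step is taken. No patients or data are added.
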